3.7 Identification of Treatments

3.7.1 Method of Assigning Subjects to Treatment Groups

After subject signs the informed consent, each site will assign potential study subjects an eight-character subject number. This number will consist of a four-digit site number (with the first two digits representing the country-specific number and the next two digits representing the site-specific number) and a three-digit subject number assigned in a sequential manner. The hyphen between the site and subject number will account for the eighth character. This number will represent the subject's identifier throughout the study. Following confirmation of eligibility at Visit 2, the Interactive Web Response System (IWRS) will be contacted by the site and it will assign the subject a four-digit randomization number that will correspond to a randomly assigned treatment group.

3.7.2 Identity of Investigational Products

3.7.3 Storage and Handling Procedures

The JTE-051 and placebo tablets should be stored at room temperature between 20 and 25°C (United States Pharmacopeia [USP]) and in a secure location with restricted access.

3.7.4 Clinical Supplies Packaging

Each site will receive a supply of double-blind study drug packaged as blister cards corresponding to 8 days of QD dosing. Each blister card will contain a total of 32 JTE-051 tablets.

Study drug blister cards may be labeled with the following information, as appropriate:

- Sponsor identity and protocol number
- Card number
- Dosing instructions
- Spaces for site personnel to add subject number and subject initials
- Spaces for site personnel to add visit number, site number and Investigator name
- Spaces for site personnel to add the card identifier, as appropriate
- Quantity and identity of contents
- Lot number and storage conditions
- Expiration date
- For investigational use only statement

The planned blister card allocation of tablets for each dose, broken down by treatment group, is provided below.

Treatment Group	Tablet 1	Tablet 2	Tablet 3	Tablet 4
JTE-051 50 mg	JTE-051 50 mg	JTE-051 Placebo	JTE-051 Placebo	JTE-051 Placebo
JTE-051 100 mg	JTE-051 50 mg	JTE-051 50 mg	JTE-051 Placebo	JTE-051 Placebo
JTE-051 150 mg	JTE-051 50 mg	JTE-051 50 mg	JTE-051 50 mg	JTE-051 Placebo
JTE-051 200 mg	JTE-051 50 mg	JTE-051 50 mg	JTE-051 50 mg	JTE-051 50 mg
Placebo	JTE-051 Placebo	JTE-051 Placebo	JTE-051 Placebo	JTE-051 Placebo

3.7.5 Administration of Study Drug

During the Treatment Period, beginning on the day of Visit 2, subjects will self-administer one dose of study drug (4 tablets) daily for 12 weeks. Study drug will be taken QD in the

morning, regardless of meals. On the scheduled study visit days, subjects should not take study drug prior to arriving to the site. At the site, study drug will be administered from the previously supplied blister card, if available, after all study procedures have been completed (except for appropriate PK samples collection procedures as discussed in [Figure 2](#)). If no tablets from the previously supplied blister cards are available, then the subject should dose from the new blister card supplied at that visit.

Randomized subjects will receive three study drug blister cards at Visits 2 and two study drug blister cards at Visit 3. Subjects will receive four blister cards each on Visits 4 and 5. The subjects will be instructed to use the blister cards on a first-in/first-out basis and to return all study drug blister cards from the former visit for accountability and compliance assessment at Visits 3, 4, 5 and 6 for accountability and compliance assessment. Following completion of accountability and compliance assessments, any unused blister card or a partially used blister card with the study drug available will be returned to the subject. At Visit 6, study drug will not be dispensed.

In the event that the subject does not take the study drug on a given day during the Treatment Period, the subject should not take more than the daily dosage on the following treatment day.

3.7.6 Management of Clinical Supplies

The Investigator will have responsibility for the control and proper distribution of all study drug (including any investigational product or reference product) in accordance with this protocol. The Investigator is responsible for ensuring that all study drug will be stored at the site at recommended storage temperatures and conditions, in a secured area, free of environmental extremes, with restricted access. The Investigator also ensures that all study drug will be dispensed only to study subjects who have provided written informed consent and have met all entry criteria.

Study drug accountability will be performed by the Investigator or designee at each study visit during the Treatment Period, according to the schedule of procedures presented in [Table 1](#). Study drug compliance will be assessed and documented per the Good Clinical Practices (GCP).

3.7.7 Randomization

Approximately 85 eligible subjects with moderate to severe plaque psoriasis will be randomized into this study. Subjects will be randomized in a 1:1:1:1 ratio (17 subjects per treatment group) to receive JTE-051 50 mg, JTE-051 100 mg, JTE-051 150 mg, JTE-051 200 mg or placebo QD. Randomization will be stratified based on prior exposure of subjects to biologic therapy (i.e., biologic treatment-naïve vs. biologic treatment-experienced subjects).

An IWRS will be employed for the randomization activities. It will use a stratified randomization algorithm that takes into account the strata specified above.

The randomization code will be controlled by an unblinded member of the Sponsor or designee who will provide the randomization code to select laboratories, see [Section 3.7.8](#).

3.7.8 Blinding

This study is double-blind (i.e., the treatment assigned to each subject will not be disclosed to the Sponsor members or designees involved in the study, study staff at the site or to the subject). The JTE-051 50 mg tablets, as well as the placebo tablets will be supplied as unbranded tablets which are identical in appearance.

The laboratory performing the JTE-051 plasma concentration assessments will be unblinded to facilitate analysis of only the samples from the JTE-051-treated subjects. Plasma samples from placebo-treated subjects may be analyzed as needed (see Section 3.5.6.32.2).

3.7.9 Breaking the Blind

The study drug code may be broken by the Investigator for a particular subject only in the event of a serious adverse experience, which the Investigator feels cannot be adequately treated without knowing the identity of the study drug by using the IWRS. Every effort must be made to contact the Sponsor's Medical Monitor prior to breaking the code. If this is not possible and the situation is an emergency, the Investigator may break the blind to identify the treatment assignment for the specific subject only and must contact the Sponsor's Medical Monitor as soon as possible thereafter. The Sponsor may also elect to break the blind for cause. If the blind is broken, appropriate documentation should be completed as soon as possible.

Additionally, breaking of the blind may be performed by sponsor designated independent member not involved in the clinical conduct of the study for regulatory reporting purposes, as appropriate.

3.8 Statistical Methods

This section provides an abbreviated statistical analysis plan (SAP) for the efficacy, safety and PK. A formal SAP will be developed at a later time. Statistical issues not addressed in this section may be developed in the formal SAP. The plans outlined in this section may be modified in the SAP; however, any major modifications of the primary endpoint definition and/or its analysis may also be reflected in a protocol amendment, as appropriate. Other deviations to the SAP will be discussed in the study report.

3.8.1 Subject Population for Analysis

3.8.1.1 Randomized Population

The randomized population consists of all subjects who are randomized at Visit 2 to one of the five treatment groups: JTE-051 50 mg QD, JTE-051 100 mg QD, JTE-051 150 mg QD, JTE-051 200 mg QD and matching placebo QD.

3.8.1.2 Safety Population

Safety population consists of the randomized subjects who receive at least one dose of the study drug and have at least one post-randomization safety data.

3.8.1.3 Intent-To-Treat (ITT) Population

The ITT population consists of the randomized subjects who receive at least one dose of the study drug per randomization and have at least one post-randomization efficacy data.

3.8.1.4 Per Protocol (PP) Population

[figure not shown]
The PP population is a subset of the ITT population in which subjects do not have any major protocol deviations. A pre-analysis meeting will take place after all data have been entered into the database and cleaned, but before the release of the randomization code, to identify the PP population. The decisions made to select the PP population will be documented.

[figure not shown]
3.8.1.5 Pharmacokinetic (PK) Population

[figure not shown]
The PK population consists of the randomized subjects who receive at least one dose of JTE-051 and have at least one usable JTE-051 plasma concentration measurement.

3.8.1.6 Sample Size

Approximately 85 eligible subjects (17 subjects in each treatment group) will be randomized into the treatment period of this study.

3.8.2 Interim Analysis

No interim analysis is planned in this study.

3.8.3 Efficacy Analyses

The ITT population will be used for all efficacy data analysis. The analysis of the primary efficacy parameter will be repeated on the PP population if it excludes 20% or more of the subjects from the ITT population. Additional efficacy analyses using the PP population may be performed if deemed appropriate.

3.8.3.1 Efficacy Parameters

The primary efficacy parameter is the proportion of subjects achieving PASI 75 at EOT.

[figure not shown]
The secondary efficacy parameters are (evaluated at Weeks 2, 4, 8, 12 and 16, unless otherwise stated):

- Percent change from baseline in PASI score;
- Proportions of subjects achieving PASI 50, PASI 75, PASI 90 and PASI 100;
- Proportion of subjects achieving a sPGA score of 0 or 1;
- Change from baseline in sPGA score;
- Percent change from baseline in the psoriasis affected BSA;
- Change from baseline in Skindex-16;

3.8.3.2 Efficacy Data Analysis

For the purpose of efficacy analysis, the EOT value is defined as the last value taken during the double-blind treatment period after the first dose of study drug, without any treatment intervention.

Conventional statistical evaluations for efficacy parameters will also be conducted as described below:

For the primary efficacy parameter (PASI 75 at EOT), the Fisher's exact test will be used to compare each JTE-051 dose group with placebo. 

For dichotomous secondary efficacy parameters, similar analyses as the primary efficacy parameter will be used by time point, [REDACTED]

[figure not shown]
[REDACTED]

For continuous efficacy parameter analysis with multiple time points, a mixed effect model will be employed. It includes fixed effects for treatment, time, treatment by time interaction, the stratification factor and the appropriate baseline and subject as the random effect. The appropriate baseline will be the parameter from which the efficacy parameter is derived, e.g., PASI score at Week 0 for the analysis of percent change from baseline in PASI score. The treatment effect of each JTE-051 dose group relative to placebo at the same time point will be estimated. A linear trend test at each time point will be computed using appropriate linear contrast.

All analyses will be performed two-sided at the 5% significance level. No formal multiple comparison adjustment will be made, therefore, results should be interpreted with the multiplicity in mind. The estimated treatment effect (relative to placebo) from the model, along with a two-sided 95% CI and p-value, will be tabulated where appropriate. The Newcombe's CI of the rate difference between JTE-051 dose and placebo will be computed when performing the Fisher's exact test. Graphical presentations of the treatment profile may be depicted. Sensitivity analysis, model fit assessment may be conducted and data transformation may be employed if appropriate.

Descriptive statistics of efficacy parameters over time will be presented by treatment. It will include the number of subjects (N), arithmetic mean, standard deviation (SD), median, minimum and maximum for continuous parameters, and in frequency tabulation form for dichotomous parameters.

[REDACTED]

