3 INVESTIGATIONAL PLAN

3.1 Number of Sites and Subjects

Multiple sites will be employed to ensure screening of sufficient number of subjects to randomize (in a 1:1:1:1:1 ratio) approximately 85 subjects (17 subjects per treatment group).

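### Does pairing an unstratified Fisher's exact test with a Newcombe interval at 17 per arm call for a different primary analysis?

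*Protocol*

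**What the plan says.** Protocol section 3.8.1.6 sets the size: "Approximately 85 eligible subjects (17 subjects in each treatment group) will be randomized". For the primary parameter, section 3.8.3.2 states that Fisher's "exact test will be used to compare each JTE-051 dose group with placebo". The interval is tied to the test: the Newcombe "CI of the rate difference between JTE-051 dose and placebo will be computed when performing the" Fisher test. The same section adds "All analyses will be performed two-sided at the 5% significance level" and "No formal multiple comparison adjustment will be made", and asks readers to bear multiplicity in mind.

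Section 3.7.7 says "Randomization will be stratified based on prior exposure of subjects to biologic therapy". That factor appears in the mixed model for continuous endpoints ("It includes fixed effects for treatment, time, treatment by time interaction, the stratification factor") but not in the visible Fisher sentence.

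Three features of the public copy matter:

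- Text is blanked straight after the Fisher sentence and again after the sentence on dichotomous secondary endpoints.
- Section 3.8.3.2 presents these conventional evaluations as additional to something else. The list of tables names simulated response rates, a distribution of the decision and a conditional go probability (Tables 8 to 10), none of which is visible.
- SAP section 5 was written after early termination with 13 subjects randomized. It cancels all inferential testing, and SAP section 4 says the ITT population will not be identified.

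**The concern.** Three things look wrong.

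- **Two methods, two verdicts.** Fisher's test is conditional and exact; Newcombe's interval is built from Wilson score limits. Near the decision boundary in small arms they can give opposite answers for the same dose, and no visible text says which one governs.
- **Lost power.** The stated level is 5%, but the test runs well below that, most of all at the low response rates likely on placebo. In a small proof-of-efficacy trial that seems wasteful.
- **Unused stratum.** A factor important enough to stratify on, and to put in the continuous model, is absent from the primary test as printed.

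At stake would be the reading of the headline result for each dose, and some power to see a real effect.

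**Working it through.** **Inputs.** From the protocol: 17 per arm, four doses against one placebo arm, two-sided 5%, no multiplicity adjustment. The documents show no response rates or stratum shares, so those below are assumptions. The stated 17 per arm cannot be reproduced, because the simulation tables are not in the public copy. All results are exact enumerations of the 18 x 18 = 324 possible tables unless noted.

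**One boundary case by hand: 4/17 against 0/17.**

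- Fisher: p = 2 x C(17,4)/C(34,4) = 2 x 2380/46376 = 0.103.
- Wilson limits: 0.0956 to 0.4726 for 4/17, and 0 to 0.1843 for 0/17.
- Newcombe lower limit: 0.2353 - sqrt[(0.2353 - 0.0956)^2 + 0.1843^2] = 0.2353 - 0.2313 = 0.004.
- Newcombe upper limit: 0.2353 + (0.4726 - 0.2353) = 0.473.

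So p is 0.10 while the interval excludes 0. The same happens at 6 v 1 (p = 0.085, 1.7 to 53.3 points) and 8 v 2 (p = 0.057, 4.5 to 58.9 points). With continuity correction, the 4 v 0 interval includes 0.

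**All tables.** With the uncorrected interval, 24 of 324 tables are discordant, always with the interval excluding 0 and p above 0.05, never the reverse. With the continuity-corrected interval, 4 of 324 are.

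**Chance of disagreement for one dose, uncorrected interval.**

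| Placebo | Dose 20% | 30% | 40% | 50% |
|---|---|---|---|---|
| 5% | 11.5% | 15.6% | 13.2% | 8.1% |
| 10% | 6.1% | 11.0% | 13.7% | 12.4% |

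When dose and placebo share one response rate, it is at most 3.3%.

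**Chance of at least one disagreement in four doses.**

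| Placebo; doses | Uncorrected | Corrected |
|---|---|---|
| 5%; 10/20/30/40% | 36.9% | 3.5% |
| 10%; 15/25/35/45% | 33.6% | 8.4% |
| 5%; 30% throughout | 48.0% | 3.7% |
| 5%; 50/60/70/75% | 12.0% | 4.7% |
| 5% in all arms | 2.0% | below 0.1% |

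**Size and power.** Fisher's two-sided size is 0.10%, 0.79% and 1.94% at common rates of 5%, 10% and 20%; the maximum is 2.44%, at 50%. The uncorrected Newcombe interval used as a test reaches 5.8%. Boschloo's unconditional test reaches 4.3%, with power against Fisher of 63.8% v 60.7% (5% v 40%), 45.7% v 39.2% (10% v 40%) and 71.5% v 62.6% (10% v 50%).

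**What the conservatism buys.** With equal arms and a common rate, half the size lies in each direction. The chance of any false claim of benefit across four doses is therefore bounded by 4 x 2.44%/2 = 4.9% for Fisher, 4 x 4.3%/2 = 8.6% for Boschloo, and 4 x 5.8%/2 = 11.6% for the interval.

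**Would stratifying cure it?** Assume 12 and 5 per arm in the two strata. The exact stratified Cochran-Mantel-Haenszel (CMH) test has a maximum size of about 2.5%, so the conservatism stays. Power is 72.4% v 72.0% for Fisher with no stratum effect (45% v 5%), and 59.6% v 54.2% with a strong one (60%/20% v 15%/2%). With 4 v 0 split 3 + 1, the exact p is 2 x [C(12,3)/C(24,3)] x 1/2 = 220/2024 = 0.109, while the stratified Newcombe lower limit is still above 0. That pairing disagrees in roughly 9-17% of comparisons, depending on the rates, the strata and how the stratified interval is built.

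**The case for a change.** The best case for a change is that the first two points rest on visible text. Fisher is the test named for the primary parameter, the interval is attached to it, and disagreement concentrates where doses work but are not overwhelming, which is what a proof-of-efficacy trial hopes to see. Boschloo's test keeps size below 5% and returns about 1 to 9 points of power with no extra subjects. Naming the interval version and the governing criterion would cost a sentence.

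The arithmetic stands, and so does the observation that the Newcombe version is unstated. The step to a defect does not:

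- **Valid, not wrong.** A size below nominal costs power but is no error. With four unadjusted comparisons the caution has a use, as the bounds show. Conditional against unconditional testing is a fair trade-off.
- **Governing criterion and stratum.** Both complaints argue from absence beside removed text. Section 3.8.3.6 refers to an analysis of dichotomous endpoints over several time points whose model is not visible, and a decision framework evidently existed. An adjusted analysis or a decision rule may be in the blanked text.
- **The alternative.** A stratified Newcombe interval beside an exact stratified CMH p-value recreates the mismatch. Making the interval decisive lets size exceed 5%.
- **Reading the result.** Since the disagreement has only one direction, a report giving both p-value and interval shows a borderline finding plainly. An analyst would take the test as the formal result and the interval as the estimate.

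**Conclusion.** No change follows. In the 85-subject plan, Fisher's test is valid and conservative (size at most 2.4%; 0.1-0.8% at common rates of 5-10%). Disagreement with an uncorrected Newcombe interval is real: about 8-16% per comparison at assumed rates of 5-10% v 30-50%, and about 34-48% for at least one of four doses at intermediate effects. It is uncommon when no dose works and much reduced with the corrected interval. The unstated interval version is a missing detail of the kind analysts settle when programming. The stratum complaint cannot be established from the public copy.

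Nor is there any gain now. The SAP runs no inferential tests. With 13 subjects over five arms (13/5 = 2.6, so 2 or 3 per arm if evenly split), the smallest Fisher p-value attainable is 2/C(6,3) = 0.10, at 3 v 0 with three per arm. No reported result depends on this choice. The figures rest on assumed response rates and stratum shares; the size results need only the 17 per arm.

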3.8.3.6 Handling of Dropouts or Missing Data

There may be missing data intermittently (i.e., a missing visit or subject dropout). For dichotomous efficacy parameters analysis by time point, subjects with missing data will not be included in the analysis. For analysis with multiple time points, any missing data will be imputed using the last observation carried forward (LOCF) method except for subjects who withdraw for reasons related to treatment. In the latter case, any value after withdrawal will

be imputed as treatment failure. For parameters analyzed both by time point and with multiple time points, these two approaches would strengthen the findings when they are similar.

For continuous efficacy parameters, no imputation will be employed. This is because the mixed effect model gives valid estimates if the missing data mechanism is “missing at random”, a common assumption made as the first approach for analysis.

For the sensitivity analysis of the primary efficacy parameter, i.e., PASI 75 at EOT, missing data may be imputed by all possible combinations of success and failure. The robustness of the finding can be evaluated using the tipping point analysis based on the plausibility of the imputed values.

Other missing data imputation methods may be employed for additional sensitivity analysis if deemed necessary.

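### Does the mixed model with subject as its only named random effect need a stated covariance structure to protect the Week 12 intervals?

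*Protocol*

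**What the plan says.** Protocol 3.8.3.2 states: "For continuous efficacy parameter analysis with multiple time points, a mixed effect model will be employed". The fixed effects are treatment, time and their interaction, and the list ends with "the stratification factor and the appropriate baseline and subject as the random effect". No residual covariance, visit-specific variance, robust standard error or degrees-of-freedom method is named in the readable text; parts of the section are blacked out. The visits are Weeks 2, 4, 8, 12 and 16 (Protocol 3.8.3.1), the last about four weeks after dosing ends. The output is by visit: "The treatment effect of each JTE-051 dose group relative to placebo at the same time point will be estimated", with 95% intervals and p-values, plus a linear trend test at each visit. Model checking is optional: "Sensitivity analysis, model fit assessment may be conducted and data transformation may be employed if appropriate".

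Protocol 3.8.3.6 imputes nothing for continuous endpoints, on the ground that "the mixed effect model gives valid estimates if the missing data mechanism is" missing at random. Protocol 3.8 describes itself as an abbreviated plan and leaves unaddressed issues to a formal SAP.

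That SAP was written after early termination. Section 5 reports 13 subjects randomized and drops inferential testing. Section 4 drops the ITT population, which Protocol 3.8.3 had assigned to all efficacy analyses. Section 5.3 only derives changes from baseline, and Section 6.1 lists no efficacy table.

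**The concern.** A subject random effect with independent residuals implies compound symmetry: equal variance at every visit and equal correlation between every pair of visits. That is doubtful for percent change in PASI. The change is zero for everyone at baseline and may fan out as some subjects respond and others do not, and Week 16 is off drug. A single pooled variance would then be too small at Week 12 and too large at Week 2. Every dose-versus-placebo interval, p-value and trend test taken from the model would inherit the error.

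The missing-data argument is also affected. A likelihood-based model is valid under missing at random only if the covariance as well as the mean is adequately modelled, and Protocol 3.8.3.6 does not mention that condition. At stake, as planned, were the visit-specific comparisons for the continuous secondary endpoints. The primary endpoint was to be analysed by Fisher's exact test and does not depend on this model.

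**Working it through.** **Inputs from the documents.** Five arms of 17: "Approximately 85 eligible subjects (17 subjects in each treatment group) will be randomized into the treatment period of this study" (Protocol 3.8.1.6). The arithmetic agrees: 5 × 17 = 85. There are five post-baseline visits, and tests are two-sided at 5%. The documents give no SD, standard error or power for a continuous endpoint, so there is no stated precision to reproduce.

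**Assumed inputs.** SDs of percent change in PASI, in percentage points, at Weeks 2/4/8/12/16, as shown in the table.

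**Formula.** With complete balanced data and treatment-by-time means, the random-intercept model pools to one total variance, the average of the five visit variances.

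- Model SE at every visit = √(2 × mean variance / 17)
- True SE at a visit = SD at that visit × √(2/17), where √(2/17) = 0.343
- Ratio = √(mean variance) / SD at that visit

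Worked case, moderate growth 15/20/28/32/32: mean variance = (225 + 400 + 784 + 1024 + 1024)/5 = 691.4, with square root 26.29. Model SE = 26.29 × 0.343 = 9.02. True Week 12 SE = 32 × 0.343 = 10.98. Ratio = 26.29/32 = 0.82.

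| Assumed SDs | Ratio, Week 2 | Ratio, Week 12 | Coverage, Week 2 | Coverage, Week 12 |
|---|---|---|---|---|
| Constant 30 | 1.00 | 1.00 | 95% | 95% |
| Mild 20/24/28/30/30 | 1.33 | 0.89 | 99.1% | 92% |
| Moderate 15/20/28/32/32 | 1.75 | 0.82 | 99.9% | 90% |
| Strong 10/15/25/35/35 | 2.61 | 0.75 | 100% | 86% |
| Falling at Week 16, 15/22/30/30/22 | 1.63 | 0.82 | 99.9% | 89% |
| Shrinking 32/30/26/22/22 | 0.84 | 1.21 | 90% | 98% |

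Coverage is of the nominal 95% interval, from 20,000 simulated trials per scenario with Satterthwaite degrees of freedom. It was nearly the same under exchangeable correlation 0.6 and AR(1) correlation 0.8, so the variance pattern drives the error. Visit-specific variances, which for complete data are equivalent to an unstructured covariance, gave 94.7% to 95.3% at every visit in every scenario. Baseline, stratum and dropout were left out, so bias under dropout was not measured.

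**Does the model produce a result in this trial?**

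- Protocol 3.8.3: efficacy analyses run on the ITT population. SAP Section 4: that population is not identified.
- Protocol 3.8.3.2: model-based effects, intervals and p-values. SAP Section 5: no inference; most data in listings only.
- Protocol 3.8.3.2: treatment profiles may be graphed. SAP Section 1: no figures. SAP 6.1: no efficacy table.

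No table, listing or figure in the SAP uses the mixed model.

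**Could the remedy be used at the size reached?** An unstructured covariance over five visits has 5 × 6 / 2 = 15 parameters; the random-intercept model has 2. With 13 subjects and all five arms occupied, 13 − 5 = 8 between-subject degrees of freedom remain, or 6 after baseline and the stratum. That is too few for a stable 15-parameter covariance.

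**The case for a change.** The best case for a change is that the specification is deficient on either reading: it means compound symmetry, or it leaves the covariance open. The protocol deferred detail to the SAP, and the SAP dropped the model without completing it. The remedy is a sentence naming an unstructured covariance, a small-sample degrees-of-freedom method and a fallback order, and 15 parameters would have been feasible at 85 subjects. The optional model-fit check is a weak safeguard, and the missing-at-random statement is incomplete as written.

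Most of this stands as a comment on the planned analysis. At the planned size, an unstructured covariance with a stated fallback would have been the better specification.

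Three parts are weaker. First, the protocol does not say that the subject effect is the only source of correlation, and it does not exclude a structured residual; the firm finding is that the covariance is unnamed. Second, the direction of error depends on a growing spread that the documents do not establish. It is argued only for PASI, whereas the model also covers sPGA, BSA and Skindex-16, and the shrinking profile makes Week 12 conservative. Third, harm under dropout follows in principle but was not quantified, because all calculations used complete data.

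None of what stands reaches a reported result, because the SAP that governs the final analysis does not fit the model.

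**Conclusion.** No change is needed, because none would bring any gain. Read with default residuals, the planned model imposes constant variance. Under the assumed growing SD profiles, Week 12 standard errors would have been 11% to 25% too small (ratios 0.89 to 0.75) and coverage 92% to 86%. With constant spread there is no error, and with shrinking spread it reverses. These sizes rest on assumed SDs, complete data and 17 subjects per arm.

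The trial stopped at 13 randomized, and the SAP reports derived changes from baseline without inference. No interval, p-value or trend test from this model will exist, so naming a covariance cannot alter a result or a conclusion. Putting an unstructured model into the SAP would contradict its decision against inferential testing and would ask 13 subjects to support 15 covariance parameters. The primary endpoint is unaffected in any case. The lesson applies to a future protocol that reuses this wording at full size.
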